Aim # 2: Determine critical neuromechanical factors influencing response to targeted or non-targeted therapy

Hypothesis: Response to targeted therapy will be associated with recovery of more normal UE movement and muscle activity patterns. **Approach:** Our measurement framework successfully allows us to target therapy. However detailed neuromechanical analysis is critical for documenting the baseline status of motor control process in order to quantify treatment-related changes in these processes. Multiple regression models will be used to determine the influence of pre- to post-intervention changes in neuromechanical factors and UE motor impairment as measured by the Rasch FMA-UE change score. This knowledge will enable further refinements of existing treatments and facilitate development of new treatments to target underlying factors.

Aim #3: Determine critical predictors of the time-course of response to rehabilitation.

Hypothesis: People with stroke have different patterns of recovery; key neuromechanical variables predict these patterns. Approach: Growth mixture modeling (GMM) will be applied to longitudinal Rasch FMA-UE measures. GMM separates a sample into subgroups of people showing similar recovery patterns, and specifies neuromechanical factors predicting these patterns. Using GMM within our measurement framework is a highly innovative method to identify distinct groups with similar recovery trajectories and describe each group's behavior in terms of FMA-UE items that can/cannot be performed over the time course of treatment.

B. BACKGROUND AND SIGNIFICANCE

Each year over 795,000 individuals in the USA have a stroke.¹ Stroke causes brain cell damage or cell death which then leads to altered patterns of connectivity in cortical and sub-cortical neural networks supporting movement.² Over 75% of stroke survivors experience some degree of upper extremity (UE) paralysis.³ Unfortunately, UE motor function rarely recovers completely; 85% of those who survive stroke report residual arm/hand motor impairment severe enough to interfere with performance of daily tasks at 4 years post-stroke.⁴

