Identifying and describing those that respond and do not respond to rehabilitation treatment is a growing area of interest in rehabilitation science. Here we aim to differentiate patterns of recovery in our sample by integrating Growth Mixture Modeling (GMM) into our Rasch FMA-UE measurement framework. This is a highly novel method for defining responders and non-responders. Although well established in educational and psychological literature, GMM is a new to rehabilitation science and has been used in only a few stroke rehabilitation studies to date.^{55,58,59}

GMM offers a robust method of identifying subgroups of people with stroke who follow distinct trajectories of UE recovery. In contrast to analyses that focus on mean-level change in a sample, GMM elucidates how different people recover in different ways. GMM separates repeated measurements of a sample into groups of individuals showing similar patterns of change over time. In addition, the analysis specifies factors predicting these distinct patterns. When placed into the Rasch FMA-UE measurement framework, the results of the GMM analysis will

enable a clear description of each subgroup because the subgroup's pattern of UE recovery will be directly connected to a description of the specific FMA-UE items that can/cannot be performed.

2h. Pilot study: targeted-rehabilitation versus non-targeted rehabilitation

Our recent pilot work³² provides evidence that a targeted rehabilitation intervention maximizes UE motor function when compared to non-targeted intervention. We conducted a pilot study (n=12, with 6 subjects per intervention group) which investigated the effects of an intervention targeted at participants with moderate post-stroke UE motor impairment, specifically those individuals who displayed reduced shoulder-elbow interjoint coordination and excessive anterior trunk flexion. The intervention was "targeted" meaning that it afforded opportunity for participants to practice a more normal reaching pattern characterized by concurrent shoulder

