Hypothesis: People with stroke have different patterns of response to therapy, some respond slowly, some respond more quickly. Key neuromechanical variables (baseline measurements of elbow extension, amount of trunk movement, and biceps-triceps muscle co-activity) predict these response patterns.

Rationale: Individuals with different levels of post-stroke UE motor impairment likely follow distinct trajectories of UE recovery. It is possible that patients receiving intensive therapy make large improvements within the first few days of therapy, and it is also possible that some patients require days until therapy has an effect. However, little is known about patterns of recovery over time in response to rehabilitation. Identifying different patterns of recovery during therapy is critical to determine which patients may need the most extensive intervention to promote functional recovery, and which patients may not require intensive intervention. In addition, it is important to identify behavioral markers that predict gains in order to improve a-priori assessments and planning for the population that is most likely to benefit from an intervention after stroke.

Approach: Growth mixture modeling (GMM) offers a robust method of identifying sub groups of people with stroke who follow distinct trajectories of UE recovery. In contrast to analyses that focus on mean-level change in a

sample, GMM elucidates how different people recover in different ways. GMM separates repeated measurements of a sample into groups of individuals showing similar patterns of change over time.

Dependent Variable: A categorical latent variable representing unobserved groupings of stroke-patients with similar patterns of change in the Rasch FMA-UE scores over repeated measurements.

[figure not shown]
Observed Variables: The Rasch FMA-UE will be administered at 5 time periods (pre-intervention, end of weeks 1,2 and 3 and post-intervention). The GMM calculates an intercept and slope of a line representing the mean and variance of the linear rate of change in Rasch FMA-UE over time. Sub-populations (or growth classes) will be displayed graphically. Each class will represent a percentage of the sample and demonstrate how the baseline Rasch FMA-UE measurement changed over time.

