Data analysis: Data from participants in targeted-rehabilitation protocols will be pooled and analyzed. Three models will be tested in accordance with our a-priori hypothesis that each level of impairment (mild, moderate, severe) should show distinct patterns of recovery, i.e., we expect 3 classes of recovery. Specifically, we will test whether there is one overall pattern of recovery that describes the entire sample (1-class), whether there are two patterns of recovery within the sample (2-class) or whether there are three patterns of recovery in the sample (3-class). The models are not nested (a 1-class model is not a subset of the 2-class model) because different individuals make up each class. Therefore the chi-square model comparison test is not appropriate. Instead, we will define the best fitting model as the one having the lowest Bayesian Information Criteria (BIC) and an entropy value closest to 1.0.

To determine the best predictors of recovery patterns we will use logistic regression to relate recovery pattern (growth class membership) to kinematic and EMG variables hypothesized to be important predictors of recovery. The predictors hypothesized to be important are baseline elbow extension AROM, amount of trunk movement, and muscle co-activity. The predictor variables entered into analysis will be collected pre-intervention. Predictors will be examined to determine those which significantly discriminate class membership. Because the predictors are allowed to vary across classes, the analysis will provide a means of examining whether predictors of one trajectory differ across each trajectory. For example, loss of elbow extension AROM may be the most significant predictor of membership in one class, while inability to activate agonist muscles may be the most significant predictor of another recovery pattern.

Methods specific to the SUBSTUDY

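### Aim 3 does not say how uncertainty in growth-class membership enters the predictor analysis; read as classify-then-regress, it understates predictor effects unless the classes separate well

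*Protocol*

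**What the plan says.** Protocol section D, Specific to Aim 3, defines the dependent variable as "A categorical latent variable representing unobserved groupings of stroke-patients". Under Data analysis, one-, two- and three-class models are fitted to the pooled targeted arms ("we expect 3 classes of recovery"), and the best model is the one with the lowest BIC and "an entropy value closest to 1.0". The next paragraph turns to prediction: "we will use logistic regression to relate recovery pattern (growth class membership) to kinematic and EMG variables". The predictors are pre-treatment elbow extension, trunk movement and biceps-triceps co-activity. They are to be tested for whether they separate the classes and then compared between trajectories: "Because the predictors are allowed to vary across classes".

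Two other places describe the link differently. Section A, Aim #3, says that the mixture model "specifies neuromechanical factors predicting these patterns". Section B, 2g, says "the analysis specifies factors predicting these distinct patterns". Both attribute the prediction to the mixture analysis rather than to a later regression.

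The Protocol mentions no posterior class probabilities, weighting or correction for classification error. Entropy serves only to choose the number of classes, and no minimum is set. The SAP covers Aim 1 and missing data only.

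**The concern.** A growth class is never observed. Each patient has a probability of belonging to each class, and assigning the most likely class makes errors wherever the trajectories overlap. A regression that takes the assigned class as the truth mixes patients from neighbouring classes, which pulls the predictor effects toward zero. Its confidence intervals are then centred on the wrong value.

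Finding baseline predictors of the recovery pattern is the purpose of Aim 3, and it will be attempted in only about 54 to 65 patients. The order of the Data analysis text (choose the classes, then regress membership) makes classify-then-regress the natural reading. An analyst following sections A and B could instead put the predictors inside the mixture model. The two procedures give different estimates from the same data, and the documents do not choose between them.

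**Working it through.** **Analysis set.** The Protocol's sample size gives 18 per group. From the pilot means, d = (2.30 − 1.42) / √((1.00² + 0.45²)/2) = 1.135, against 1.13 stated. A two-sided t-test at alpha 0.05 and 90% power with d = 1.13 needs 17.48, that is 18 per group, so the figure reproduces. Aim 3 uses the targeted arms only: 3 × 18 = 54 planned completers, or 130/2 = 65 if half of those enrolled are counted. No power, effect size or classification quality is stated for Aim 3, so the settings below are assumptions.

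**Why assignment attenuates.** Take two equally common classes, a true log-odds ratio β, and error rate e unrelated to the predictor given true class. The probability of being assigned to class 2 is e + (1 − 2e)p(x), and at p = 0.5 its slope on the logit scale is (1 − 2e)β. For two normal classes separated by 2, 3 or 4 SD, e = Φ(−1) = 0.159, Φ(−1.5) = 0.067 and Φ(−2) = 0.023. The factors are therefore 0.68, 0.87 and 0.95. Attenuation is greater away from the midpoint, so a fitted model falls somewhat below these.

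**Large-sample size, two classes.** Simulation of 200,000 persons, β = 1.0 per SD, known class parameters, most-likely-class assignment. Ranges are over two separate runs.

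| Entropy | Estimate from assigned class | Loss |
|---|---|---|
| 0.49 | 0.61–0.63 | 37–39% |
| 0.64 | 0.73–0.74 | 26–27% |
| 0.76 | 0.82–0.83 | 17–18% |
| 0.85 | 0.88–0.89 | 11–12% |
| 0.91 | 0.94 | 6% |

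At entropy 0.49, a true odds ratio of e^1.0 = 2.72 per SD would be reported as about e^0.62 = 1.86.

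**Three classes, five visits.** This is closer to the plan. Slopes are equally spaced, intercept variance is 1, slope SD 0.1, residual SD 0.4, and the log-odds ratio between adjacent classes is 1.0. Entropy is 1 + Σ p log p / (N log 3).

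| Entropy | Assignment error | Estimated / true |
|---|---|---|
| 0.98 | 0.7% | 0.99 |
| 0.84 | 7% | 0.90 |
| 0.56 | 22% | 0.73 |
| 0.24 | 39% | 0.39 |

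In a separate three-class simulation with purely random misclassification, multinomial logistic regression recovered the true effects when class was known (ratio 1.00 to 1.01).

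**At the planned size.** With n = 60, two classes and β = 1.0, nominal 95% intervals from the assigned class covered the true value in 73–74% of runs at entropy 0.48–0.49, 83% at 0.64 and 90–92% at 0.76. With true class known, coverage was about 95%. One-step and bias-adjusted three-step estimates averaged about 1.0, with 94–97% coverage.

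**Power at n = 60 (5% likelihood-ratio test, 600 runs).** At separations of 2, 3 and 4 SD, assigned class gave 57%, 82% and 92%. Bias-adjusted three-step gave the same 57%, 82% and 92%. One-step gave 67% and 86% at 2 and 3 SD. The SD of the three-step estimate rose from 0.33 to 0.88 at 2 SD and from 0.36 to 0.57 at 3 SD.

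**The case against.** The strongest reply is that the documents never say that patients are assigned to a class first. The outcome is defined as latent, sections A and B attribute prediction to the mixture analysis, and regressing latent class on covariates inside a mixture model is itself a logistic regression. A figure beside the Aim 3 model description is not shown and might settle the matter. This stands as far as it goes: classify-then-regress is the natural reading of the Data analysis text, not its literal wording. It does not remove the point, because the text allows either procedure.

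A reader might also infer that logistic regression cannot serve three classes. The documents do not support that. Logistic regression includes the multinomial form, and the plan expects predictors to act differently across classes. Only the word multinomial and a reference class are missing.

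Third, the plan prefers high entropy, and at 0.98 the loss is about 1%. That is true, but no minimum is set, and entropy competes with BIC in choosing the model.

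Fourth, with no true effect the assigned-class test rejected 4–6% of the time, so false positives were not inflated in these settings. That stands. The damage is to effect sizes and interval coverage.

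**Conclusion.** The plan leaves open how uncertainty in class membership reaches the predictor estimates, and its most natural reading ignores that uncertainty. If the most likely class is used uncorrected, the loss ranges from negligible at entropy near 1.0, through about 10% at 0.84 to 0.85, to nearly 40% at 0.49, with interval coverage at n = 60 falling to about 74%.

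These sizes rest on assumed class separations, an assumed log-odds ratio of 1.0, class parameters taken as known, and classification error unrelated to the predictors given true class. Estimating the classes in about 60 patients adds further uncertainty, and error related to the predictors could bias in other directions. It would therefore be too strong to say that the effects will be biased toward zero.

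It would also be too strong to say that a correction would uncover predictors otherwise missed. With class known, power was about 92%, against 58%, 71% and 80% from the assigned class (entropy 0.49, 0.64 and 0.76). Most of that gap is information lost to class overlap: three-step recovered none of it in the power comparison and one-step only part.

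The Aim 1 treatment comparison is unaffected. The point is still worth acting on, because it concerns the central inference of a stated aim.

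**What to change.** In the Protocol's Aim 3 Data analysis, or in an Aim 3 section added to the SAP:

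- State that latent class is regressed on the three baseline predictors by logistic regression, multinomial with a named reference class if three classes are retained.
- Choose in advance between estimation inside the mixture model (one-step) and a bias-adjusted three-step method. One-step was the more precise at this sample size, but it lets the predictors influence how the classes form. Three-step keeps the two apart, at the price of larger variance when entropy is low.
- Report entropy and estimated classification error with the predictor results, and use the most likely class for description only.
- Bring sections A and B (2g) into line with the chosen method.

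The cost is wording and suitable mixture software, with no change to data collection or sample size. Intervals will be wider, and with 54 to 65 patients the results should be presented as estimates with limited power.

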Sample size was calculated based on FMA-UE data obtained from our pilot study (see Preliminary Studies) to determine whether there is a statistical difference in people receiving targeted rehabilitation vs. a comparison non-targeted intervention in the present parallel arm design with 6 treatment groups. Specifically, we will test $H_0: \mu_{\text{targeted}} = \mu_{\text{non-targeted}}$, versus the two tailed alternative $H_a: \mu_{\text{targeted}} \neq \mu_{\text{non-targeted}}$. The pilot study demonstrated that the targeted (trunk restraint) group exhibited a post-training Rasch-derived FMA-UE person ability measure of 2.30 (± 1.00) logits, while the non-targeted intervention (mCIMT) group exhibited a post-training Rasch FMA-UE score of 1.42 (± 0.45) logits which yields a Cohen's d effect size of 1.13. With an alpha level = 0.05, for a two-tailed hypothesis test at a 90% power level, the sample size calculation specified that 18 individuals are needed in each group to answer the research hypothesis confidently. With 6 treatment groups,

Group data (not presented) suggested that participants demonstrated expected UE movement patterns prior to the intervention in that while attempting to reach forward they had difficulty extending the elbow while flexing the shoulder. Participants who underwent an intervention specifically aimed at altering this movement pattern demonstrated a statistically significant Pre to Post gain in voluntary elbow extension ranges of motion whereas those who underwent an intervention that was not aimed at altering the compensatory movement pattern showed very little gain in voluntary elbow extension. For example 4 out of 5 participants in the targeted treatment group showed increased elbow extension angular excursion, while 4 out

N=108. Based on the stroke rehabilitation literature we anticipate a 20% drop out rate and therefore will enroll **N=130** subjects.

Project Timeline:

	Jan	Feb	Mar	Apr	May	Jun	Jul	Aug	Sept	Oct	Nov	Dec
Yr1					Preparation and Recruitment					Enroll 20 patients		
Yr2								Enroll 48 patients				
Yr3								Enroll 40 patients				
Yr4				Complete follow-up tests					Data analysis and manuscript preparation			

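### Aim 3 tests its baseline predictors only on growth-class membership: no test is possible if one class is selected, and classes that follow starting level say little about rate of recovery

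*Protocol*

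**What the plan says.** All of this is in the protocol, Research Design and Methods, under Specific to Aim 3. The hypothesis concerns speed of response, with three baseline variables said to predict the pattern: "some respond slowly, some respond more quickly. Key neuromechanical variables (baseline measurements of elbow extension, amount of trunk movement, and biceps-triceps muscle co-activity) predict these" … The Observed Variables paragraph describes a growth model over five administrations of the Rasch FMA-UE: "The GMM calculates an intercept and slope of a line representing the mean and variance of the linear rate of change in Rasch FMA-UE over" … The declared dependent variable, however, is a categorical latent class.

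The Data analysis paragraph pools the targeted-arm patients and compares one-, two- and three-class models, choosing by lowest BIC and entropy nearest 1.0. Three classes are expected because there are three impairment levels. The first model tests "whether there is one overall pattern of recovery that describes the entire sample (1-class" in the plan's shorthand). The predictors then enter in one place: "we will use logistic regression to relate recovery pattern (growth class membership) to kinematic and EMG variables hypothesized to be important predictors of recovery".

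No alpha, power or effect size is given for Aim 3. The SAP covers Aim 1 only.

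**The concern.** The hypothesis is about rate and the growth model estimates a rate with a variance, but the predictors are never related to that rate. Two consequences follow.

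- **One class selected.** Class membership has a single level and logistic regression cannot be fitted. Patients may still differ in rate, and a baseline variable may explain the difference, but the plan has no analysis that would show it.
- **Two or three classes selected.** Classes form on intercept and slope together. The sample is stratified by baseline Rasch FMA-UE, so the classes can separate patients by where they started. A predictor of class is then a marker of severity, not of speed of response.

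In either case the purpose of Aim 3, finding predictors of the time-course, could go unmet with all the data in hand.

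**Working it through.** **1. The plan's own sample size (Aim 1).** The inputs are "2.30 (± 1.00) logits" (targeted) and "1.42 (± 0.45) logits" (non-targeted). Pooled SD = √((1.00² + 0.45²)/2) = √0.60125 = 0.7754. d = (2.30 − 1.42)/0.7754 ≈ 1.13, matching the stated "effect size of 1.13". The plan specifies: "With an alpha level = 0.05, for a two-tailed hypothesis test at a 90% power level". The two-sample t-test has 89.1% power with 17 per group and 90.9% with 18, so 18 is reproduced. This sizing is for Aim 1; Aim 3 takes what it yields.

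**2. Patients available to Aim 3 (targeted arm).** Planned completers: 3 × 18 = 54. Enrolled, assuming equal allocation: 130/2 = 65. After the anticipated 20% dropout: 130 × 0.80/2 = 52.

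**3. Is there a fallback?** Aim 2 regresses percent change in FMA-UE on pre-to-post changes in the neuromechanical variables, not on their baseline values. The SAP stops at Aim 1. Neither tests the baseline-predictor hypothesis.

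**4. Power if the slope itself is analysed.** Calculated for one of three predictors, two-sided 0.05:

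| Partial r | N = 54 | N = 65 |
|---|---|---|
| 0.30 | 62% | 70% |
| 0.37 | 82% | 88.5% |
| 0.45 | 95% | 98% |

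**5. Simulation assumptions.** None of these is in the documents: SD of true gain 0.7 logits, visit error SD 0.35, slope-predictor correlation r of 0.37 or 0.45, and a predictor unrelated to baseline. One-, two- and three-class mixtures were fitted to each patient's intercept and slope. BIC chose the number of classes, and the predictor was tested on modal class. A one-class result counts as no rejection. There were 150-300 runs per setting, with Monte Carlo error of about 3-4 points.

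**6. Cost of cutting alone** (N = 54, r = 0.37, continuous slopes). Linear regression 76-81%; median split 61-66%; tertiles 61-65%; 80/20 split 48-51%. Within a given baseline shape the loss runs from about 11 points (76.0 − 65.3) to 33 points (81.0 − 48.3).

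**7. Planned route, continuous slopes, N = 54.**

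| Assumed baseline | Classes selected | Planned route | Slope, r = 0.37 | Slope, r = 0.45 |
|---|---|---|---|---|
| Normal | one, 96% of runs | about 1% | 81% | 93% |
| Uniform | one, 54-56% | 4-5% | 76% | 93% |
| Three severity clusters | three, 67-71% | 6-7% | 79% | 93% |

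In the last row classes are usually found, but they follow starting level. A separate set of runs (gain SD 0.5-1.0, r = 0.45, 18 patients per severity stratum, slope regression adjusted for baseline) selected one class in about 19-35% of runs. Power was about 5-13% for the planned route and 60-88% for the slope. The least favourable slope result, 52%, came from a normal baseline with gain SD 0.5 and a correlation of 0.4 with the true rate.

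**8. Two real slope classes, N = 54.**

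| Baseline | Gap (logits) | Planned route | Slope |
|---|---|---|---|
| Normal | 1.0 | 3.5% | 56% |
| Normal | 1.5 | 47% | 69% |
| Normal | 2.0 | 83% | 80% |
| Severity clusters | 1.5 | 25% | 69% |
| Severity clusters | 2.0 | 68% | 73% |

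For scale, the mean gain in the pilot's targeted group was 2.30 − 0.90 = 1.40 logits.

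**9. If the predictor is related to baseline.** Preliminary Studies 3e reports that elbow range of motion differs between all severity categories. With an assumed predictor-baseline correlation of 0.7, slope-regression power of 59-97% unadjusted falls to 52-81% after adjusting for baseline.

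**The case against.** The strongest reply is that Aim 3 sets out to find responder subgroups. Its dependent variable is declared categorical, and to say that it cuts a continuous rate presumes there are no subgroups, which is the question being asked. A one-class result would itself answer the first half of the hypothesis. This stands as a reason to keep the growth classes. It does not supply a test for the second half, on predictors.

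A reader might infer that one class will usually be selected. The documents do not support that. It follows from a normal baseline like the pilot's, 0.90 (SD 1.01), and the pilot enrolled moderate impairment only. With mean 0.90, SD 1.0 and Table 4's cut-points, 54 patients would divide into about 3 mild (54 × P(z > 1.54) = 54 × 0.062) and 7 severe (54 × P(z < −1.12) = 54 × 0.131), against 18 planned in each. With strata filled as planned, one class is the minority result. Power stays low in those runs for the other reason: the classes follow baseline.

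A reader might also infer that categorising in itself loses most of the power. Step 6 shows that it does not, and with widely separated classes and a normal baseline nothing is lost.

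Three limits remain. A figure in the Aim 3 description is not shown, so any predictor paths drawn there cannot be seen; the text describes none to the slope. The simulations apply BIC without the entropy half of the selection rule. Most of the slope-regression figures are unadjusted and assume a predictor unrelated to baseline, which step 9 shows is favourable.

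**Conclusion.** The concern holds in a limited form. Two parts rest on the text alone: class membership is the only outcome on which the baseline predictors are tested, and a listed result, one class, leaves that test impossible with nothing in its place. A third part is a reasoned expectation: where classes track impairment level, the test speaks mainly to severity.

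The size is conditional. With continuous recovery, about 54 completers and a predictor unrelated to baseline, the planned route has roughly 1-13% power against roughly 50-90% for the slope. The gap narrows as real slope classes separate, and at about 2 logits apart it disappears under a normal baseline. The SD of gain, the visit error, the baseline distribution and the predictor correlations are all assumed, so these figures show the possible range and do not forecast this trial. The change is a cheap improvement to the plan's ability to answer Aim 3; the class analysis is not invalid.

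**What to change.** Pre-specify in the protocol and SAP, alongside the class analysis, a growth or mixed model that relates each patient's FMA-UE slope to baseline elbow extension, trunk movement and biceps-triceps co-activity (in a mixed model, the time-by-predictor terms). Use all five occasions, adjust for the baseline measure or impairment level, and report the result whatever number of classes is selected. Keep the growth classes, and run the class-membership regression only if two or more are selected. State the alpha for the predictor tests and the power expected at the available sample size.

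The cost is protocol and SAP wording and one extra model on measurements already planned. The predictor result would be expressed in logits per week in addition to class odds.
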